## 5.7.6. Prohibited Medications

The following medications are prohibited during the treatment period of the study:

- Any concurrent anticancer therapy (eg, chemotherapy, radiation therapy, surgery, immunotherapy, biologic therapy) intended to treat malignancy relapse or recurrence. Maintenance therapy with TYK inhibitors for high-risk Philadelphia chromosome-positive leukemia and FLT3 inhibitors for FLT3+ acute myeloid leukemia may be used with sponsor approval.
- Any secondary GVHD therapy due to insufficient response/progression on study treatment.
- Concomitant use of targeted therapies with anti-GVHD activity, including but not limited to tumor necrosis factor alpha inhibitors and IL-6 receptor inhibitors.

- Concomitant use of a JAK inhibitor.
- Initiating therapy with an investigational medication unless otherwise approved by the medical monitor.
- Receipt of live (including attenuated) vaccines during the first year of study.

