### **4.4. Duration of Treatment and Subject Participation**

After signing the ICF, screening assessments will be completed over a period of up to 28 days. Subjects will receive study treatment in continuous 28-day cycles; this may include temporary treatment interruptions described in Section 5.6.3. Each subject enrolled in the study may continue to receive study treatment as long as benefit is being observed and/or treatment withdrawal criteria are not met. If the subject permanently discontinues study treatment (see Section 5.6.5 for details), the treatment period will end, and the subject will enter the follow-up period. The safety follow-up visit will occur 30 to 35 days after the last dose or EOT visit (whichever is later), and the post-treatment GVHD and survival follow-up periods will last until death or study withdrawal. Study participation is expected to average approximately 12 months per individual subject but may vary based on clinical outcomes.

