## **5.4. Prophylactic and Supportive Care Medications**

Patients who undergo allo-HSCT are at risk for a variety of infections based on the degree of immunosuppression induced by the conditioning regimen before transplant. As such, it is considered routine practice to use antibiotics, anti-infectives, and immunizations as prophylactic therapies ([Tomblyn et al 2009](#)). In cases where post-transplant anti-infective prophylaxis measures are necessary, ongoing therapy may continue at the investigator's discretion per institutional guidelines.

Systemic and topical GVHD prophylaxis medications (eg, cyclosporine, methotrexate, tacrolimus) may be continued at therapeutic doses as appropriate based on stage and sites of disease.

Additional supportive care measures (eg, use of antimotility agents for diarrhea management, beclomethasone, ursodiol) are permitted at the investigator's discretion.

See Section [5.7.4](#) for additional details.

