**Table 5: Schedule of Assessments**

Visit Day Item	Section	Screening	Treatment a											EOT d	Re-Treatment e	Follow-Up			
			-28 to -1	D1	D7	D14	D21	D28	D35	D42	D49	D56 b	D100	D180	D365 c	Safety f	GVHD g	Survival h	
Informed consent	7.1	X																	
Inclusion/exclusion criteria	3	X	X																
Contact IRT	7.2	X	X				X				X	X		X	X				
Demography/disease history	7.3	X																	
Prior/concomitant medications	7.4	X													X	X	X		
Supportive care medications	5.4	X													X	X	X		
AE assessment	7.5.1	X													X	X	X		
Physical examination	7.5.2	X	X	X	X	X	X	X	X	X	X	X		X	X	X			
Height and weight i	7.5.2	X	X j	X	X	X	X	X	X	X	X	X		X	X	X	X		
Vital signs	7.5.3	X	X j	X	X	X	X	X	X	X	X	X		X	X	X			
ECOG and Lansky scale performance status	7.5.4	X	X j	X	X	X	X	X	X	X	X	X		X	X	X			
12-lead ECG	9.5.4	X	X j												X				
aGVHD grading and response	7.6.1	X	X j												X	X	X	X	
cGVHD assessment	7.6.2	X													X	X	X	X	
Chimerism assessment/graft failure	7.6.3	X	X j																
PTLD assessment	7.6.4																		
Underlying disease relapse assessment	7.6.5	X	X j																
Dispense study drug	5.1			X				X				X			X		X		
Study drug compliance	5.5			X				X				X			X	X	X		
Steroid dose monitoring	5.3	X													X	X			
Survival follow-up	6.5.3																	X	
New GVHD therapies	6.5.2																		X

ECG = electrocardiogram; PTLD = post-transplant lymphoproliferative disorder.

a A ± 3-day window is permitted to facilitate scheduling during the treatment phase.

b After Day 56, visits will occur every 28 days and will include all Day 56 assessments.

c The Day 365 visit will also serve as the regularly scheduled visit occurring every 28 days after Day 56 (ie, Day 364).

d A ± 7-day window is permitted. A second EOT should occur if the subject restarts itacitinib and subsequently discontinues treatment.

e Re-treatment assessments occur every 28 days ± 3 days.

f 30 to 35 days after EOT.

g Every 8 weeks  $\pm$  7 days after EOT. Acute GVHD assessments are required every 28 days  $\pm$  7 days during survival follow-up for subjects who completed study treatment or discontinued early withdrew for reasons other than GVHD progression of GVHD.

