## **6.2. Treatment**

The treatment period begins on the day that the subject receives the first dose of study drug through the point at which the principal investigator at the study site determines that the subject will be permanently discontinued from study drug. Dates for subsequent study visits will be determined based on this day and should occur within  $\pm$  3 days of the scheduled date unless delayed for safety reasons. During the Day 1 visit, results from screening visit evaluations should be reviewed to determine whether the subject continues to meet the eligibility requirements as specified in the Protocol.

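### The on-treatment ban on live vaccines lapses after one year, but itacitinib dosing has no time limit

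*Combined protocol and SAP*

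**What the plan says.** Section 5.7.6 opens with "The following medications are prohibited during the treatment period of the study". Its last item is "Receipt of live (including attenuated) vaccines during the first year of study". No other item in the list has a calendar limit.

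The treatment provisions contain no matching limit:

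- Section 4.4: a subject "may continue to receive study treatment as long as benefit is being observed", unless withdrawal criteria are met. Dosing is in continuous 28-day cycles, and "this may include temporary treatment interruptions described in Section 5.6.3".
- Section 4.1.2 ends treatment on failure, unacceptable toxicity, a completed taper or death. The mandatory withdrawal criteria in Section 5.7.1 include no time limit.
- Table 5, footnote b: "After Day 56, visits will occur every 28 days and will include all Day 56 assessments". Footnote c: "The Day 365 visit will also serve as the regularly scheduled visit occurring every 28 days after Day 56". Day 365 is listed under Treatment and is not described as the end of it.
- Section 5.6.4 permits, but does not require, a taper from Day 180 in a child in CR or VGPR who has been off corticosteroids for at least 8 weeks. A further step may follow 28 to 56 days later.
- Section 6.4 allows one re-treatment course after a completed taper, with no latest start and no maximum length.

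The only other rule on live vaccines is exclusion criterion 11 in Section 3.2, which excludes children who have received one or are expected to need one during the study.

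**The concern.** The lead-in to Section 5.7.6 already confines the list to time on treatment, so the first-year phrase cannot add cover beyond it and can only take some away. Once a child passes one year, the ban ends while dosing may continue.

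This is a safety rule for study conduct. Section 1.5 ties the possible increase in infections to itacitinib therapy, not to time since enrollment. Section 5.4 says of transplant recipients that "it is considered routine practice to use antibiotics, anti-infectives, and immunizations as prophylactic therapies" and does not separate live from inactivated vaccines. A site that consults Section 5.7.6 for a child on drug at, say, Day 400 finds no prohibition.

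Re-treatment adds a second uncertainty. Section 6.2 runs the treatment period "through the point at which the principal investigator at the study site determines that the subject will be permanently discontinued from study drug", and Section 5.6.4 treats what follows a completed taper as a separate re-treatment period. It is therefore unclear whether the list covers re-treatment at all.

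**Working it through.** The plan gives no figure to reproduce. The gap follows from the text: the ban stops at one year, nothing stops dosing at one year, and a child benefiting in PR does not meet the default taper condition. The day counts below show how readily a child on the default schedule crosses that point.

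**Inputs and assumptions**

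- The first year is taken to end on Day 365, counted from each child's Day 1. The protocol does not anchor it.
- Taper begins no earlier than Day 180 and no earlier than 56 days (8 weeks) after steroids stop (Section 5.6.4).
- Two taper steps, full dose to 50% to off (Table 4), separated by *s* = 28 to 56 days (Section 5.6.4).
- No sponsor-approved early taper.

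**First course.** If steroids stop on day X, the default taper ends no earlier than X + 56 + *s*. Dosing passes Day 365 when X > 365 − 56 − *s*:

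- *s* = 28: X > 365 − 56 − 28 = Day 281
- *s* = 56: X > 365 − 56 − 56 = Day 253

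**Re-treatment.** The earliest default end of the first course is Day 180 + *s*. The earliest re-treatment start is the next day. The re-treatment days that fit through Day 365 are 365 − start + 1.

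| Quantity | *s* = 28 | *s* = 56 |
|---|---|---|
| First course ends | 180 + 28 = Day 208 | 180 + 56 = Day 236 |
| Re-treatment Day 1 | Day 209 | Day 237 |
| Re-treatment days through Day 365 | 365 − 209 + 1 = 157 | 365 − 237 + 1 = 129 |

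A re-treatment course longer than 157 or 129 days runs past the ban, and a later start leaves fewer days.

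**Full default re-treatment course.** Section 6.4 mentions Day 180 for taper during re-treatment but does not say whether that is study Day 180 or re-treatment Day 180. If it is re-treatment Day 180 (an assumption):

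| Quantity | *s* = 28 | *s* = 56 |
|---|---|---|
| Re-treatment Day 180 | 209 + 179 = Day 388 | 237 + 179 = Day 416 |
| Earliest end of re-treatment | 388 + 28 = Day 416 | 416 + 56 = Day 472 |
| Days past Day 365 | 416 − 365 = 51 | 472 − 365 = 107 |

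On that reading, a completed default re-treatment course always outlasts the ban. Early taper, treatment failure or toxicity would shorten it.

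**Whether other text closes the gap.** Criterion 11 is applied at entry and looks forward to a need foreseen then. It does not tell a site what to do when a vaccine is first considered in year 2. No other text in the protocol prohibits live vaccines during treatment.

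**The case against.** The strongest reply is that little is left uncovered. Criterion 11 has no one-year limit, so read literally it already keeps out a child whose need for a live vaccine in year 2 can be foreseen. What remains is an unforeseen need, after one year, in a child still on drug. Sites would also not decide on a live vaccine for an immunosuppressed transplant recipient from Section 5.7.6 alone: investigator judgment applies (Section 5.7.1), Section 5.4 cites an infection-prevention guideline, and the Investigator's Brochure (Section 8.6), which is not available here, may carry a warning. All of this stands as a reason to grade the point low. None of it supplies the missing rule.

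A second reply is that if re-treatment lies outside the treatment period, the Section 5.7.6 lead-in drops every prohibition during re-treatment, so the lead-in is what needs repair. If re-treatment lies inside, naming it is unnecessary. The text supports either reading. Naming re-treatment in this bullet does no harm on one reading and helps on the other, but the same doubt does hang over the rest of the list.

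Third, the proposed wording sets no interval after the last dose and leaves the first year unanchored. Both are fair suggestions for additions; neither makes the change wrong.

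Finally, the day counts are earliest-case bounds, not estimates of how many children are affected. That is correct. The conclusion rests on the absence of a dosing cap, not on those counts.

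**Conclusion.** The concern holds. As written, the explicit live-vaccine ban ends at one year while itacitinib may continue in a first course or in re-treatment, and no other provision in the protocol fills the gap. That conclusion needs only the reading that the first year ends at Day 365. The 51-to-107-day overrun for a full default re-treatment course also needs Day 180 in Section 6.4 to mean re-treatment Day 180, and the finding does not depend on it.

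The importance is minor. The number of children affected is not given and is probably small: Section 4.4 expects participation to average about 12 months. Day 28 ORR, the DLT rule, PK and precision do not change. The point is worth correcting because it is a safety prohibition in transplanted children and the correction is cheap.

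**What to change.** Extend the last bullet of Section 5.7.6. Keep its present words, "Receipt of live (including attenuated) vaccines during the first year of study", and add: *and, beyond that, at any time while on itacitinib treatment, including dose interruptions and re-treatment.* Leave exclusion criterion 11 as it is.

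This keeps all the existing first-year cover, including any that applies after a child stops drug within the year. Simply deleting the first-year phrase could lose that cover and would leave re-treatment in doubt.

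Three optional additions: state that the first year is counted from each child's Day 1; name re-treatment in the Section 5.7.6 lead-in so that the whole list clearly applies to it; and set an interval after the last dose, whose length the sponsor would have to justify because the documents give no basis for one.

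The cost is one bullet, with no extra visits, data or subjects. The only downside is a delayed live vaccine for the few children still on drug after one year.

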## 6. STUDY ASSESSMENTS

All study assessments will be performed as indicated in the schedule of assessments (see [Table 5](#)) and all laboratory assessments will be performed as indicated in [Table 6](#). [Table 7](#) presents a summary of clinical laboratory analytes to be assessed. The order of assessments is suggested by the order of mention within the schedule. See Section [7](#) for instructions on each assessment. Further details of study procedures and assessments can be found in the study reference manual.

**Table 5: Schedule of Assessments**

Visit Day Item	Section	Screening	Treatment a											EOT d	Re-Treatment e	Follow-Up			
			-28 to -1	D1	D7	D14	D21	D28	D35	D42	D49	D56 b	D100	D180	D365 c	Safety f	GVHD g	Survival h	
Informed consent	7.1	X																	
Inclusion/exclusion criteria	3	X	X																
Contact IRT	7.2	X	X				X				X	X		X	X				
Demography/disease history	7.3	X																	
Prior/concomitant medications	7.4	X													X	X	X		
Supportive care medications	5.4	X													X	X	X		
AE assessment	7.5.1	X													X	X	X		
Physical examination	7.5.2	X	X	X	X	X	X	X	X	X	X	X		X	X	X			
Height and weight i	7.5.2	X	X j	X	X	X	X	X	X	X	X	X		X	X	X	X		
Vital signs	7.5.3	X	X j	X	X	X	X	X	X	X	X	X		X	X	X			
ECOG and Lansky scale performance status	7.5.4	X	X j	X	X	X	X	X	X	X	X	X		X	X	X			
12-lead ECG	9.5.4	X	X j												X				
aGVHD grading and response	7.6.1	X	X j												X	X	X	X	
cGVHD assessment	7.6.2	X													X	X	X	X	
Chimerism assessment/graft failure	7.6.3	X	X j																
PTLD assessment	7.6.4																		
Underlying disease relapse assessment	7.6.5	X	X j																
Dispense study drug	5.1			X				X				X			X		X		
Study drug compliance	5.5			X				X				X			X	X	X		
Steroid dose monitoring	5.3	X													X	X			
Survival follow-up	6.5.3																	X	
New GVHD therapies	6.5.2																		X

ECG = electrocardiogram; PTLD = post-transplant lymphoproliferative disorder.

a A ± 3-day window is permitted to facilitate scheduling during the treatment phase.

b After Day 56, visits will occur every 28 days and will include all Day 56 assessments.

c The Day 365 visit will also serve as the regularly scheduled visit occurring every 28 days after Day 56 (ie, Day 364).

d A ± 7-day window is permitted. A second EOT should occur if the subject restarts itacitinib and subsequently discontinues treatment.

e Re-treatment assessments occur every 28 days ± 3 days.

f 30 to 35 days after EOT.

g Every 8 weeks  $\pm$  7 days after EOT. Acute GVHD assessments are required every 28 days  $\pm$  7 days during survival follow-up for subjects who completed study treatment or discontinued early withdrew for reasons other than GVHD progression of GVHD.

h Every 8 weeks  $\pm$  7 days.

i [REDACTED]

j If a screening assessment was performed within 3 days of Day 1, it does not need to be repeated on Day 1.

**Table 6: Laboratory Assessments**

Visit Day Item	Section	Screening	Treatment a												EOT e	Re-Treatment f	Safety Follow-Up g	GVHD Follow-Up h									
		-28 to -1	D1 b	D7	D14	D21	D28	D35	D42	D49	D56 c	D100	D180	D365 d													
Chemistry panel h	7.5.6.1	X	X	X	X	X	X	X	X	X	X i	X i	X	X	X	X	X j										
Hematology h	7.5.6.2	X	X	X	X	X	X	X	X	X	X i		X	X	X	X											
Hepatitis screening	7.5.6.4	X k																									
HIV screening	7.5.6.5	X k																									
Adenovirus, CMV, and EBV blood DNA-PCR	7.5.6.6		X l	X m										X	X m												
Serum pregnancy test (childbearing females only); may apply only to Cohort 1	7.5.6.3	X													X												
Urine pregnancy test n (childbearing females only); may apply only to Cohort 1	7.5.6.3		X																								
PK assessment h,o	7.7		X p	X			X p																				

a A ± 3-day window is permitted to facilitate scheduling during the treatment period.

b Day 1 laboratory assessments do not need to be repeated if screening assessments were performed within the preceding 7 days, except for PK.

c After Day 56, visits will occur every 28 days and will include all Day 56 assessments.

d The Day 365 visit will also serve as the regularly scheduled visit occurring every 28 days after Day 56 (ie, Day 364).

e A ± 7-day window is permitted. A second EOT should occur if the subject restarts itacitinib and subsequently discontinues treatment.

f Re-treatment assessments occur every 28 days ± 3 days.

g 30 to 35 days after EOT.

h Efforts should be made to use the minimal possible blood volume for performing these tests.

i Does not need to be repeated if test is performed within 7 days.

j Liver testing including total bilirubin.

k Test results before transplantation are acceptable.

l PCR test results are not required for subject eligibility.

m To be performed weekly as long as GVHD is active and then as clinically indicated.

- n Urine pregnancy tests are required every 28 days.
- o Phase 1: Samples to be collected at 1 hour  $\pm$  15 minutes, 2 hours  $\pm$  30 minutes, 4 hours  $\pm$  30 minutes, 6 hours  $\pm$  30 minutes, and 12 hours  $\pm$  60 minutes (12 hours only if inpatient) on Days 1, 7, and 28 and at predose on Days 7 and 28. Phase 2: Samples to be collected at predose, 1 hour  $\pm$  15 minutes, 2 hours  $\pm$  30 minutes, and 4 hours  $\pm$  30 minutes on Day 7.
- p The PK assessment may be performed solely on Day 7 if blood volume sampling limits prohibit sampling on all 3 PK days.
- q [REDACTED]
- r Day 56 only.

**Table 7: Clinical Laboratory Analytes**

Serum Chemistries	Hematology a	Other
Albumin	Hematocrit	Serum pregnancy test b
Alkaline phosphatase	Hemoglobin	Urine pregnancy test b
ALT	Mean corpuscular volume	
AST	Reticulocytes	
Bicarbonate or CO 2	Platelet count	
Blood urea nitrogen	Red blood cell count	
Calcium	White blood cell count	
Chloride	White blood cell differential (5 parts):	Hepatitis and HIV Screening Testsc
Creatinine	
 
• Basophils
 
• Eosinophils
 
• Lymphocytes
 
• Monocytes
 
• Neutrophils
 
	Hepatitis B surface antigen Hepatitis B surface antibody Hepatitis B core antibody HCV antibody HCV-RNA HBV-DNA HIV
Glucose		Adenovirus, EBV, and CMV Assessments
Lactate dehydrogenase		Adenovirus-DNA EBV-DNA CMV-DNA
Lipid profile (total cholesterol, high-density lipoprotein, low-density lipoprotein, and triglycerides)		
Phosphorus		
Potassium		
Sodium		
Total bilirubin		
Total protein		

ALT = alanine aminotransferase; AST = aspartate aminotransferase; CMV= cytomegalovirus; EBV= Epstein-Barr virus; HBV = hepatitis B virus; HCV = hepatitis C virus.

a Hematology and chemistry assessments will be performed locally.

b May be applicable to Cohort 1 only.

c Test results obtained before transplantation are acceptable.

All possible measures should be taken to reduce pain and discomfort (eg, use of local anesthesia before venipunctures, noninvasive measure should be preferred and timing coordinated with daily activities as far as possible; [European Commission 2017](#)). Physical pain and discomfort intensity must be assessed and regularly monitored and treated according to local appropriate guidance (eg, ethical considerations for clinical studies on medicinal products conducted with minors), particularly in neonates and children who cannot express it verbally. In order to minimize pain, discomfort, and fear, facilities should be appropriate to childcare, and the personnel should be trained to look after children and supervised by experienced health care professionals. The investigational site's staff should be trained to communicate with both the parents/legally designated representative and the children.

The degree of burden and risk threshold will be constantly monitored by the investigator.

## **6.1. Screening**

The screening period is the interval between signing the ICF and the date of first dose of study treatment (Cycle 1 Day 1). The screening period may not exceed 28 days. Informed consent must be obtained from each subject (parent or legal guardian) before performing any study-specific procedures that are not considered standard of care. Assessments that are required to demonstrate eligibility may be performed over the course of 1 or more days during the screening process.

Procedures conducted as part of the subject's routine clinical management (eg, complete blood count) and obtained before signing of informed consent may be used for screening or baseline purposes, provided that the procedure meets the Protocol-defined criteria and has been performed within 28 days before the first day of study drug administration. All information associated with eligibility requirements must be entered into the appropriate eCRF pages.

Results from the screening visit evaluations will be reviewed to confirm subject eligibility before enrollment/administration of study treatment. [REDACTED] chimerism results are not mandatory for enrollment decision. Tests with results that fail eligibility requirements may be repeated during the screening period if the investigator believes the results to be in error or believes that eligibility status has changed (eg, following recovery from an infection). For screening assessments that are repeated, the most recent available result before administration of study drug will be used to determine subject eligibility.

## **6.2. Treatment**

The treatment period begins on the day that the subject receives the first dose of study drug through the point at which the principal investigator at the study site determines that the subject will be permanently discontinued from study drug. Dates for subsequent study visits will be determined based on this day and should occur within  $\pm$  3 days of the scheduled date unless delayed for safety reasons. During the Day 1 visit, results from screening visit evaluations should be reviewed to determine whether the subject continues to meet the eligibility requirements as specified in the Protocol.

